## PROTOCOL TITLE: *SQEASI: Systematized Quality Exercise Alternatives for Stress Incontinence*

with 80% power. Allowing for a dropout of 20% we will enroll at least 50 patients (or 25/group), but up to 75 total.

This is a not a multi-center study. Data will be housed at the Eubank clinic

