### 7. Study Endpoints

The **primary endpoint** of our study is to determine the 3 month change in ICIQ-SF score between the women who undergo PFPT compared to those who undergo home biofeedback therapy for stress urinary incontinence. Our secondary endpoints include patient report of symptomatic cure or improvement and cost effectiveness between techniques and cost of intervention. Our **exploratory endpoints** are to investigate compliance with treatment between groups, preference if given choice between options, and differences in sexual function 3 months after initiation of therapy between the two groups. Desire for further treatment will also be assessed.

Given the extremely low-risk nature of the therapeutic interventions, we do not have any **safety endpoints**.

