## **12. Study Procedures**

This non-blinded, non-inferiority randomized controlled trial will be conducted at the UNM Eubank Clinic and SRMC Urogynecology clinic. Each site will recruit participants and we will plan to obtain up to 75 between the two sites. Collaborating investigators will be members of the Urogynecology Division at UNM HSC.

The primary aim of our study is to determine if quality of life is improved with use PFPT versus home biofeedback therapy alone in women with SUI. The target population will be patients with SUI who are seeking care. The current recommendation is to advise patient undergo conservative management with PFPT, try an incontinence pessary, or request the patient perform exercises at home. For all patients who present for treatment of SUI, we will take a thorough history and physical (including a POP-Q pelvic examination), score vaginal muscle strength based on Modified Oxford Grading Scale, perform a cough stress test to assess for SUI, and counsel the patient on all of her options including medical and surgical interventions.

If the patient is interested in conservative management and fulfills study inclusion criteria, we will then offer her the choice of volunteering for the study. All women will give written consent prior to their enrollment at this time and fill out questionnaires in the clinic. Research staff and clinicians will obtain consent and administer study questionnaires. After enrollment, participants will fill out baseline surveys, including the International Consultation on Incontinence Questionnaire- Short form (ICIQ-SF), Incontinence Severity Index (ISI), European Quality of Life-5 dimensions (EQ-5D), Overactive Bladder Questionnaire short form (OAB-q SF) Pelvic Organ Prolapse Incontinence Sexual Questionnaire (PISQ-12), and Female Sexual Function Index (FSFI). Data collected in addition to the above outcome measures includes patient demographics, medical/surgical History, and contact information, which are attached as supporting documents. This information will be collected from the patient on the day of enrollment and we will review the patient's medical record if information is missing or unclear.

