Three months after starting active treatment, all participants will have a return visit to discuss progress, which is consistent with our standard care for these patients. If the participant had a delay in starting PFPT, the follow up visit will occur 3 months after first PT appointment. At the 3 month visit the patient will complete the ISI, ICIQ-SF, EQ-5D, OAB-q SF, PISQ-12, FSFI, and PGI-I. We will also ask the patient which treatment she would prefer if given the option, the level of satisfaction she has with the current treatment, and if she is planning any future surgical procedures or treatment for her stress incontinence. A physical exam will assess pelvic floor strength using the Modified Oxford Grading Scale and a cough stress test will be performed. If the patient is unable to return to clinic, a member of the research team will call the patient to administer the surveys over the phone. If unable to contact the patient 3 times, we will discontinue attempts and the patient will be considered lost to follow up.

Table 1: Outcomes collected at various time points

	Baseline	3 months
Demographic and medical history	X	
ISI	X	X
Revised Oxford Scale	X	X
ICIQ-SF	X	X
EQ-5D	X	X

FSFI	X	X
OAB-q SF	X	X
PISQ-12	X	X
PGI-I		X
Follow up Questionnaire		X

Our primary outcome is changes in QOL at 3 months after treatment initiation as measured by the ICIQ-SF. It is our standard of care to see patients back at 3 months following SUI treatment initiation to assess for continued leakage and offer further conservative or surgical management. Therefore, as part of a secondary aim we will assess sexual function, compliance with treatment between groups, preference between 2 options, and desire for further treatment at this 3 month time point.

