## **13. Data Analysis**

Data Analysis: Between and within group differences will be evaluated using Fisher's exact test for categorical variables and t-tests for continuous variables. If there are any baseline differences between groups, a multivariate analysis will determine the contribution of these differences to observed differences (if any) between groups.

Power Analysis: Power analysis was performed based on previously reported means and standard deviation for the ICIQ-SF questionnaire. The primary outcome of this study is improvement in incontinence quality of life as measured by the ICIQ-SF Questionnaire. We used the previously reported means and standard deviation for this questionnaire (10) from a prior RCT on biofeedback and pelvic floor exercises. We have assumed a change score of greater than 4 points to be significant between groups based on prior studies and the minimally important difference that has been previously established (11). To achieve significance for a non-inferiority study using these assumptions we would need 42 patients, 21 per group to detect this difference with alpha =0.05 and with 80% power. To allow for a dropout of 20% we will enroll at least 50 patients, but up to 75 to account for participants who are lost to follow up.

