**III. Medical Devices**

The PeriCoach© biofeedback device will be used to measure pelvic floor muscle strength and provide guidance for patients to improve their pelvic floor exercises. These devices will be

PROTOCOL TITLE: *SQEASI: Systematized Quality Exercise Alternatives for Stress Incontinence*

provided for the 25 patients randomized to the biofeedback arm at the cost of the investigators. The devices are Bluetooth connected to the patient's smartphone and their profile collects password protected data based on the frequency and quality of their exercises on a secure smartphone application. We will request that the patient show researchers their profile at the 3 month visit to determine the frequency and quality of their exercise performance. The device has already been tested and validated for measuring pelvic floor muscle strength and treating female urinary incontinence and hence, its safety and effectiveness are not being evaluated in this study.

The FDA letter is attached.

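### The primary ICIQ-SF change gets an unadjusted t-test, with adjustment only if the arms look different at baseline and no rule on which result decides non-inferiority; a pre-specified baseline-adjusted model would settle this and usually gain power

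*Combined protocol and SAP*

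**What the plan says.** Section 7 sets the primary endpoint: "to determine the 3 month change in ICIQ-SF score between the women who undergo PFPT compared to those who undergo home biofeedback therapy". Section 12 repeats it: "Our primary outcome is changes in QOL at 3 months after treatment initiation as measured by the ICIQ-SF". Section 13 names no test for ICIQ-SF specifically. Its general rule is Fisher's exact test for categorical variables and "t-tests for continuous variables", and nothing else in the plan is assigned to the primary endpoint, so the t-test applies to it by implication.

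The only covariate adjustment is conditional: "If there are any baseline differences between groups, a multivariate analysis will determine the contribution of these differences". The sentence goes on to say that the contribution meant is to whatever difference is observed between the arms. It does not define a difference, list the variables to be examined, specify the model or rank the two results. Section 13 also gives no confidence-limit rule against the 4-point margin.

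Baseline ICIQ-SF is available. Under Section 12, "participants will fill out baseline surveys, including the International Consultation on Incontinence Questionnaire- Short form (ICIQ-SF") and other instruments, and Table 1 of that section schedules ICIQ-SF at baseline and at 3 months.

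**The concern.** There are two separate problems.

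1. **No deciding analysis.** The verdict depends on one confidence limit set against 4 points. The crude and adjusted analyses can fall on opposite sides of that margin in the same data. If both exist and neither is named as decisive, the choice can be made after the results are seen, in an unmasked trial.

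2. **An inefficient default and a data-driven trigger.** After proper randomisation any baseline difference is chance, so a check for differences is a poor reason to adjust. The reason to adjust for baseline ICIQ-SF is that it predicts the 3-month score, and that holds whether or not the arms happen to balance. Subtracting baseline, as a change score does, fixes the baseline slope at 1. A model estimates the slope and usually leaves less residual variance. With about 20 evaluable women per arm at the minimum enrolment, that precision matters.

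**Working it through.** **Inputs from the documents.** Margin 4 points, 21 per group, alpha 0.05 (sidedness not stated), 80% power and 20% dropout (Sections 5 and 13). Enrolment: "Allowing for a dropout of 20% we will enroll at least 50 patients (or 25/group), but up to 75 total". The device section plans for 25 women in the biofeedback arm.

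**Inputs the documents do not give.** The SD, whether it belongs to the change or to the raw score, and the correlation r between baseline and 3-month ICIQ-SF. These are assumed below and varied.

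**Step 1: the plan's own figure.** With true difference zero, n per arm = 2(z₁₋α + z₀.₈₀)² SD² / 4². Because no SD is stated, solve backwards from n = 21:
- One-sided 0.05: SD² = 21 × 16 / (2 × (1.645 + 0.842)²) = 336 / 12.37 = 27.2, so SD = 5.21 (5.12 with the t distribution).
- One-sided 0.025: SD² = 336 / (2 × (1.960 + 0.842)²) = 336 / 15.70 = 21.4, so SD = 4.63 (4.51 with the t distribution).

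The figure of 21 can be reached but not verified.

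**Step 2: completers.** 50 × 0.80 = 40, or 20 per arm. 75 × 0.80 = 60, or 30 per arm.

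**Step 3: relative variance.** Let k be the 3-month SD divided by the baseline SD. The variance of the adjusted estimate relative to the change-score estimate is

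k²(1 − r²) / (1 + k² − 2rk), which is (1 + r)/2 when k = 1.

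| k | r = 0.3 | r = 0.5 | r = 0.7 |
|---|---|---|---|
| 0.8 | 0.50 | 0.57 | 0.63 |
| 1.0 | 0.65 | 0.75 | 0.85 |
| 1.3 | 0.81 | 0.91 | 0.99 |
| 1.5 | 0.87 | 0.96 | 1.00 |

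**Step 4: power at 20 per arm, change SD 5.21, one-sided 0.05.** As a hand check, the t-test standard error is 5.21 × √(2/20) = 1.648, and 4/1.648 − 1.645 = 0.78, so power is about 78% by the normal approximation. At k = 1 and r = 0.5 the adjusted standard error is 1.648 × √0.75 = 1.427, and 4/1.427 − 1.645 = 1.16, or about 88%. Simulation with t critical values (100,000 trials per scenario, bivariate normal scores) gives slightly lower figures:

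| Analysis | r = 0.3 | r = 0.5 | r = 0.7 |
|---|---|---|---|
| t-test on change | 77% | 77% | 77% |
| Adjusted model, k = 0.8 | 95% | 93% | 91% |
| Adjusted model, k = 1.0 | 90% | 86% | 82% |
| Adjusted model, k = 1.3 | 83% | 79% | 76% |
| Adjusted model, k = 1.5 | 81% | 77% | 76% |
| Adjust only if baseline ICIQ-SF differs at p<0.05, k = 1.0 | 78% | 78% | 77% |

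The p<0.05 trigger in the last row is an assumption, since the plan sets no threshold. Across all the SD ratios that rule adds at most about 2 points.

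**Step 5: error and disagreement, same setting.**
- Type I error (true difference 4): the t-test and the adjusted model each give 4.9–5.1%. The conditional rule gives 4.1–5.1%, so it does not inflate error.
- If whichever analysis passed could be reported, type I error would be 7.5%, 7.1% and 6.7% at k = 1 (5.5–8.0% across SD ratios).
- Opposite verdicts (true difference 0): 16%, 13% and 10% of trials at k = 1 (4–20% across SD ratios).

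**Step 6: other settings, k = 1.**
- 30 per arm, SD 5.12: t-test 91%, adjusted model 98%, 96%, 94%. Opposite verdicts fall to about 5–8%.
- One-sided 0.025, SD 4.51, 20 per arm: t-test 78%, adjusted model about 92%, 88%, 83%.
- If 5.21 is the raw-score SD, the change SD becomes 5.21 × √(2(1 − r)). At 20 per arm and one-sided 0.05, t-test against adjusted power is 64% v 79%, 77% v 86% and 93% v 95%.

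**Step 7: how often the trigger could fire.** If a difference meant p<0.05 on any of 10 independent baseline variables, chance alone would set it off in 1 − 0.95¹⁰ = 40% of trials.

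**The case against.** **The sentence can be read as explanatory.** On that reading the t-test is the main comparison and the multivariate analysis only helps interpret it. This is a natural reading, but the plan does not state it. If it is right, the remaining point is that the less efficient analysis is primary.

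**The written plan does not inflate type I error.** This stands. The t-test holds its level, and so does the conditional rule when triggered by baseline ICIQ-SF. The figures of 6.7–7.5% are hypothetical: they apply only if the favourable result may be chosen afterwards. The plan neither permits nor rules that out.

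**The gain rests on quantities the documents do not give.** This also stands. If the SD is that of the raw score, the gain runs from about 15 points at r = 0.3 to 2 or 3 at r = 0.7. If the 3-month SD is 1.3 to 1.5 times baseline, the result runs from 6 points gained to about 1 lost. A usual gain is a fair description; a guaranteed one would not be.

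**Enrolment may reach 75.** Power is then 91% with the t-test and the practical gain is smaller. The missing decision rule remains at any enrolment.

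**A change score already uses baseline.** True, but with a fixed slope of 1, which is seldom the most efficient value.

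**Conclusion.** The concern holds. Section 13 does not name the analysis that decides non-inferiority. It makes adjustment depend on observed imbalance, and its default leaves available precision unused. This does not invalidate the t-test.

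At the minimum enrolment with equal SDs, pre-specified adjustment is worth about 5 to 13 power points (77% to 82–90%). Adjusting only after a baseline difference is seen recovers at most about 2. The choice of analysis would change the verdict in 10–16% of trials when the arms are truly equal.

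These sizes assume 20 completers per arm, one-sided alpha 0.05, a change SD of about 5.2 and r between 0.3 and 0.7. They vary with the SD ratio and shrink at 30 per arm. The absence of a decision rule depends on none of these assumptions. The sponsor should make the change, although the trial remains analysable without it.

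**What to change.** Replace the conditional sentence in Section 13 with text such as:

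> The primary analysis is a linear model of 3-month ICIQ-SF on treatment arm and baseline ICIQ-SF, fitted regardless of observed balance. Non-inferiority is concluded if the upper confidence limit for the adjusted difference (biofeedback minus PFPT, signed so that positive is worse for biofeedback) is below 4 points. The limit is one-sided 95% if the sample-size alpha of 0.05 is one-sided, or one-sided 97.5% if it is two-sided [state which]. No covariates are selected by baseline testing.

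Keep the unadjusted comparison of change as a sensitivity analysis that does not decide non-inferiority.

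The endpoint is unaffected: with baseline in the model, analysing change or the 3-month score gives the same treatment difference and the same standard error.

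The cost is one short paragraph and one degree of freedom, worth about 1 power point or less. No new data are needed.

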### **Comparative Cost Analysis**

The cost analysis will be conducted from a societal and patient perspective and will be expressed as incremental cost required to produce one additional unit of quality-adjusted life year (QALY). Data on each subject's use of medical and non-medical resources related to stress urinary incontinence care will be collected during the follow up period. Direct and indirect costs of care in the physical therapy group will be compared to the at home biofeedback group. We plan to capture incremental direct health care, direct non-medical, and indirect resource use related to study interventions and incontinence care using surveys.

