### *Rationale for using the EQ-5D to measure Utility Values*

The European Quality of Life-5 Dimensions (EQ-5D) is a preference-based utility index algorithm will be used to calculate each subject's utility index (13). This instrument will be collected at baseline and 3 months. The EQ-5D has 5 attributes (mobility, self-care, usual activities, pain/discomfort and anxiety/depression) with 3 levels each for a possible 243 unique health states. Using the scoring function based on time-tradeoff method we will compare change in QALYs between the two treatment groups. We are choosing to use a general scale to calculate change in utilities (rather than condition-specific) to allow for comparison of cost-effectiveness results with other interventions and diseases, and this instrument has been validated in women with pelvic floor disorders.

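### The combined cost-effectiveness result is stated only as a cost-per-QALY ratio, with no interval method and no rule for a QALY difference near or below zero

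*Combined protocol and SAP*

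**What the plan says.** The Comparative Cost Analysis (Section 13) takes a societal and a patient perspective and says the result "will be expressed as incremental cost required to produce one additional unit of quality-adjusted life year (QALY". This is the only form given for cost and effect combined. Section 7 lists cost effectiveness among the secondary endpoints.

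The two components are also to be compared separately. On cost: "Direct and indirect costs of care in the physical therapy group will be compared to the at home biofeedback group". On effect, the EQ-5D subsection says "we will compare change in QALYs between the two treatment groups", and of the EQ-5D itself, "This instrument will be collected at baseline and 3 months". The same subsection gives comparability with other interventions and diseases as the reason for choosing a generic utility measure.

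The general methods in Section 13 are Fisher's exact test, "t-tests for continuous variables", and a multivariate analysis if the arms differ at baseline. The sample size, "21 per group to detect this difference with alpha =0.05 and with 80% power", is set for the ICIQ-SF. On enrolment: "we will enroll at least 50 patients, but up to 75 to account for participants who are lost to follow up".

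Section 1 hypothesises equal improvement in quality of life, measured by the ICIQ-SF (Aim 1), and lower cost with similar success for home biofeedback (Aim 2). It states no hypothesis about the EQ-5D or QALYs.

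**The concern.** A cost-per-QALY ratio behaves well only when its denominator is clearly different from zero. If the two treatments perform alike, as the investigators expect for ICIQ-SF and success, the estimated QALY difference will fall either side of zero largely by chance. The ratio can then be very large in either direction.

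Its sign is also ambiguous on its own. A negative value can mean cheaper and better, or dearer and worse. A positive value can mean dearer and better, or cheaper and worse.

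The t-tests give an interval for the cost difference and another for the difference in QALY change. They give none for the quotient or for the two jointly. The plan states no bootstrap, net-benefit analysis, willingness-to-pay value, dominance rule, or instruction for a QALY interval that includes zero. At stake is a secondary endpoint: a point value could be published and set against other interventions although the data do not support a ratio.

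**Working it through.** **What can be reproduced.** The plan gives no figure for the cost-effectiveness analysis. Its one design figure, 21 per group, cannot be confirmed because the ICIQ-SF standard deviation is not stated. With a 4-point margin, a true difference of zero and 80% power, it implies an SD of about 5.1 to 5.2 at one-sided 0.05, or about 4.5 to 4.6 at one-sided 0.025. Here it is used only as the number analysed per arm.

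**Inputs from the documents.** EQ-5D at baseline and 3 months (0.25 year); 21 analysed per arm; up to 75 enrolled with 20% dropout, so 75 × 0.8 = 60, or 30 per arm.

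**Assumptions, not in the documents.**
- EQ-5D utility SD 0.1 to 0.2, and baseline-to-3-month correlation r of 0.3 to 0.7.
- Linear interpolation between the two readings. The plan does not say how QALYs will be formed. Under this assumption QALY change = 0.5 × 0.25 × utility change = 0.125 × utility change, so a utility difference of 0.04 at 3 months is worth 0.005 QALY.

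**Standard error of the between-arm difference in QALY change.**

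SE = 0.125 × SD × √(2(1 − r)) × √(2/n)

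For example, SD 0.1, r 0.7, n = 21: 0.125 × 0.1 × √0.6 × √(2/21) = 0.00299.

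**When the ratio has a bounded interval.** A 95% Fieller interval is bounded only if the observed QALY difference exceeds 1.96 × SE in absolute value. With true difference d, the chance that it is unbounded is Φ(1.96 − d/SE) − Φ(−1.96 − d/SE).

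| n per arm | SD, r | SE (QALY) | Bounded only above (QALY) | As a utility difference | Unbounded at d = 0.005 |
|---|---|---|---|---|---|
| 21 | 0.10, 0.7 | 0.0030 | 0.006 | 0.05 | 61.3% |
| 21 | 0.15, 0.5 | 0.0058 | 0.011 | 0.09 | 86.1% |
| 21 | 0.20, 0.3 | 0.0091 | 0.018 | 0.14 | 91.5% |
| 30 | 0.10, 0.7 | 0.0025 | 0.005 | 0.04 | 48.4% |
| 30 | 0.20, 0.3 | 0.0076 | 0.015 | 0.12 | 90.0% |

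At d = 0 the figure is 95% whatever the SD. That holds by construction of a 95% interval and is not evidence about this trial.

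**Effect of adjusting for baseline EQ-5D.** SE = 0.125 × SD × √(1 − r²) × √(2/n) gives 0.0028 to 0.0074 at n = 21. The unbounded share at d = 0.005 becomes 56% to 90%. Adjustment helps but does not remove the problem.

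**Illustration in dollars (all values assumed).** Take biofeedback minus PFPT: cost difference −$100 (SE $40), QALY difference 0 (SE 0.006), uncorrelated. In simulation the central 95% of ratio estimates runs from about −$266,000 to +$265,000 per QALY, give or take a few thousand dollars of simulation error. The sign is a coin toss.

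Incremental net monetary benefit on the same inputs is +$100, with SE = √(40² + (λ × 0.006)²), where λ is willingness to pay per QALY:

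- λ = $20,000: SE 126.5, 95% interval −$148 to +$348
- λ = $50,000: SE 302.7, −$493 to +$693
- λ = $100,000: SE 601.3, −$1,079 to +$1,279

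These intervals are bounded and their sign can be read, but all include zero.

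**The case against.** The strongest reply is that the ratio is not the only economic output. Costs and QALY changes are each to be compared, so a reader given both can see which quadrant the result lies in. In the dollar illustration, where biofeedback is clearly cheaper, only 0.6% of negative ratios are dearer and worse; with a smaller or noisier assumed cost difference (−$50 with SE $40, or −$100 with SE $100) the share is 10.6% or 15.9%. This largely answers the sign ambiguity. It does not supply an interval for the combined result or say what to report when the QALY difference is indistinguishable from zero.

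A reader might infer that the plan itself predicts a zero denominator. It does not. The equality hypotheses concern the ICIQ-SF and success rates, and a near-zero EQ-5D difference is an inference from them, made more likely by the 3-month horizon and small arms.

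A reader might also infer that the free device would be costed at nothing. The documents do not support that. The plan seeks to capture "indirect resource use related to study interventions and incontinence care using surveys", which concerns resource use, not prices, and the Medical Devices checklist says the investigators bear the device cost.

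Finally, every magnitude above rests on outside assumptions, the plan does not propose a Fieller interval, and net benefit adds no precision. All true. The ranges are declared, and the gap in the plan exists whatever the values. Net benefit is one accepted presentation among several; its advantage is a bounded, readable result.

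**Conclusion.** The concern holds in limited form: a cheap improvement to a secondary endpoint. The plan fixes the combined result as a ratio, without an interval method and without a rule for a QALY difference near or below zero. If the arms perform alike, that ratio will be unstable. With 21 per arm, and under the stated EQ-5D and interpolation assumptions, its 95% Fieller interval would be unbounded in roughly 61% to 91% of trials at a true difference of 0.005 QALY. With 30 per arm the range is roughly 48% to 90%.

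A reader might conclude that the whole economic analysis is uninterpretable. The documents do not support that: the separate cost and QALY comparisons stand, the hypothesis that biofeedback is less expensive can still be tested, and the primary endpoint is untouched.

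**What to change.** In the Comparative Cost Analysis, before results are known:

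1. Make incremental cost and incremental QALYs (adjusted for baseline EQ-5D, with the QALY calculation stated) the main result, each with an interval.
2. Add incremental net monetary benefit over a stated range of willingness-to-pay values, with a bootstrap cost-effectiveness plane for the joint uncertainty.
3. Report the cost-per-QALY ratio only beside these, and not as a stand-alone point estimate when the QALY interval includes zero.

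The cost is a few sentences in Section 13, a willingness-to-pay range to choose, and a little more analysis. No patients, visits or data items are added. The downside is that a single cost-per-QALY figure may not be reportable, and the result will be openly imprecise: the change makes it readable but adds no precision.
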